6.4.4. Concomitant Medications and Non-Drug Treatments

Concomitant medications and non-drug treatments received by patients during the study will be summarized for the SA set by Cohort.

Concomitant medications refer to all medications which started prior to first dose of study treatment and continued during the on-treatment period (see [Section 5.2](#)) as well as those started during the on-treatment period. Concomitant medications will be coded in the WHO Drug coding dictionary and will be tabulated by Anatomical Therapeutic Chemical (ATC) Classification level 2 and preferred term in descending order of frequency in the lorlatinib arm. In case of equal frequency regarding drug class (respectively drug name), alphabetical order will be used. A patient will be counted only once within a given drug class and within a given drug name, even if he/she received the same medication at different times. Preferred Terms will be reported under each ATC class that it is included under within WHO Drug (no primary path is available in WHO Drug).

Concomitant non-drug treatments refer to all non-drug treatments administered during the on-treatment period. Non-drug treatments will be coded with the most current version of MedDRA and will be summarized by MedDRA's SOC and PT in descending order of frequency in the lorlatinib arm. Patients will be counted only once per PT even if he/she received the same treatment multiple times.

Any medications or non-drug treatments, aside from anti-cancer treatments described in [Section 6.4.1](#) which were only administered prior to treatment start will be listed but not summarized.

6.4.5. Subsequent Anti-Cancer Therapies/Procedures

Subsequent Anti-Cancer Therapies and Procedures are defined as therapies entered on the 'Follow-up Cancer Therapy', 'Follow-up Radiation Therapy', and 'Follow-up Surgery' CRF pages. The number and percentage of patients within each category (medication therapy, radiation therapy, and surgeries) will be provided by Cohort.

Medications will be coded using the WHO Drug coding dictionary and will be tabulated by preferred term in descending order of frequency on the study treatment.

Analyses will be based on the FA population by Cohort.

6.5. Safety Summaries and Analyses

Unless otherwise specified, summaries of AEs and other safety parameters will be based on the safety analysis set by Cohort and Total.

6.5.1. Adverse Events

All analyses will be based on treatment emergent events unless otherwise specified. Treatment emergent is defined in [Section 3.5.1](#). AEs not considered treatment emergent will be flagged in data listings.

A high level summary of adverse events will include the number and percent of patients with:

- Any Adverse Event;
- Serious AE;
- Adverse Events with CTCAE Grade 3-4;
- Grade 5 events;
- AEs leading to dose interruptions;
- AEs leading to dose reductions;
- AEs leading to withdraw.

Additionally, the number of any AE will be provided. Each unique adverse event at the PT level in each Cohort of the study for a patient is included in the count.

Seriousness, toxicity grade, action taken (interruption, reduction, and withdraw) are as reported by the investigator on the adverse event CRF.

Summaries by Cohort, SOC and PT in decreasing frequency based on the frequencies observed in each Cohort will be provided for:

- Treatment Emergent Events by Maximum Toxicity Grade (All Causality);
- Treatment Emergent Events by Maximum Toxicity Grade (Treatment Related);
- Serious Treatment Emergent Events (All Causality);
- Serious Treatment Emergent Events (Treatment Related).

An event will be considered treatment related if the investigator considered the event related to the study drug or this information is unknown.

The following summaries will be provided by Cohort and PT/clusters of AEs (ie, summaries will not include SOC) in decreasing frequency based on the frequencies observed in the study treatment for:

- Treatment Emergent Events (All Causality) by Preferred Term (including Clusters of Preferred Term) and Maximum Toxicity Grade;
- Treatment Emergent Events (Treatment Related) by Preferred Term (including Clusters of Preferred Term) and Maximum Toxicity Grade;
- Treatment Emergent Grade 3-5 Events (All Causality) by Preferred Term (including Clusters of Preferred Term) and Maximum Toxicity Grade;
- Treatment Emergent Adverse Events Leading to Dose Interruptions by Maximum Toxicity Grade (All Causality);
- Treatment Emergent Adverse Events Leading to Dose Reductions by Maximum Toxicity Grade (All Causality);
- Treatment Emergent Adverse Events Leading to Permanent Withdraw by Maximum Toxicity Grade (All Causality);
- Serious Treatment Emergent Events (All Causality).
- Serious Treatment Emergent Events (Treatment Related).

Each patient will be counted only once within each PT.

As described in [Section 5.3](#) in case a patient has events with missing and non missing toxicity grades, the maximum of the non-missing grade will be displayed. Missing grade will only be displayed in the event that only one event has been reported for a patient and the grade is missing.

6.5.1.1. Adverse Events of Special Interest

These analyses will be performed for treatment emergent AEs of special interest as specified in [Section 3.5.2](#).

- **Time to AE Onset (in days)** is defined as the time from the date of the first dose to the onset date of the AE, regardless of grade. If a patient has multiple episodes of an AE, the date of the first occurrence is used. Time to AE onset (in days) will be calculated as (AE start date – first dose date +1). Time to onset is calculated for the subgroup of patients who had the specific AE
- **Time to Grade 3 or 4 AE Onset (in days)** is defined similarly as time to AE onset for Grade 3 or 4 AEs.
- **Duration of AE (in days)** is defined as the cumulative duration across episodes of the AE, regardless of grade, where duration for each episode is the time from the AE start date to the AE end date. For one episode, duration (in days) = AE end date – AE start date + 1. If a patient has multiple episodes of an AE, cumulative duration across all episodes will be used adjusting for any overlap. If a patient has an AE that was ongoing at the time of analysis, the time is censored at the last available on treatment visit date. Duration is calculated for the subgroup of patients who had the specified AE.

Descriptive statistics will be presented for time to AE onset (days), time to Grade 3 or 4 AE onset, and duration of AEs for the subgroup of patients with the AE.

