CNS effects could be categorized into 3 different categories including cognitive effects, mood effects and speech effects, which have been reported separately. The treatment related including cognitive effects, mood effects and speech effects have been observed in 21.7%, 15.3%, 8.1% patients in the 100-mg pooled group of Study 1001. The most common treatment related AEs in each category are memory impairment and irritability, slow speech, each occurring in 9.5%, 5.8% and 3.4% patients.

The CNS effects reported in both Phase 1 and Phase 2 portions have been generally considered mild (Grade 1 and Grade 2) in severity and transient, and improved upon dose delay and/or dose reduction. No Grade 4 or 5 CNS effects have been reported in the Phase 1 or Phase 2 portions. A more detailed evaluation of CNS effects is ongoing in the Phase 2 portion by routine assessment of cognition, mood, and suicidality through a computerized test (using laptops provided by Cogstate). Based on the preliminary results observed, the assessments in this Phase 2 study will be limited to mood and suicidality.

Changes in QTc and PR prolongation have also been observed in the study. QT interval prolongation was reported as treatment related AE in 5.4% patients in the 100-mg pooled group of Study 1001. And no Grade 3, Grade 4, Grade 5 treatment related AE have been reported. There were no atrioventricular block events in Phase 1, Grade 1 atrioventricular block was reported in 2 patients in Phase 2 as treatment related AE. No Grade 2 and above treatment related atrioventricular block have been reported. Basing on the preliminary evidence, the assessment of ECG and heart function will be conducted in this Phase 2 study.

In the 100-mg pooled group of Study 1001, 11.3% patients had a maximum decrease from baseline in LVEF $\geq 20\%$. The mechanism for the LVEF decreases is currently unclear, and it will need be further explored. Thus, the decrease of LVEF will also be evaluated in this study.

Peripheral neuropathy, mood disorders, cognitive disorders, speech disorders, vision disorders, diarrhoea, constipation, arthralgia, oedema, fatigue, weight increased are identified risks associated with lorlatinib administration, for which dose delay and/or dose reduction have been effective.

For complete details of the nonclinical/clinical studies, refer to lorlatinib current investigator's brochure

Efficacy

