5.2.15. Analyses for Continuous Data

Continuous variables will be summarized using descriptive statistics ie, number of non-missing values and number of missing values [ie, n (missing)], mean, median, standard deviation (SD), minimum, maximum and first and third quartile (Q1 and Q3). CCI [REDACTED] PK summaries will also include coefficient of variation percent (%CV).

In case the analysis refers only to certain visits, percentages will be based on the number of patients with an assessment at that visit, unless otherwise specified.

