5.2.17. Analyses for Time to Event Data

Time to event endpoints will be summarized using the Kaplan-Meier method and estimated survival curves will be displayed graphically when appropriate. Graphs will describe the number of patients at risk over time. The median, first and third quartiles, and probabilities of an event at particular points in time will be estimated by the Kaplan-Meier method. Confidence intervals for medians and quartiles are based on the Brookmeyer-Crowley¹ method. Confidence intervals for the estimated probability of event at a particular timepoint will be generated using the log(-log) method with back transformation to a confidence interval on the untransformed scale. Summaries of the number and percentages of patients with an event will also be provided on summary tables and/or figures.

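### SAP 6.5.1.1 pools censored and completed AESI durations in one descriptive summary and plans no count of unresolved events (minor, descriptive safety table only)

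*SAP*

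**What the plan says.** SAP 6.5.1.1 defines AESI duration in days for every patient who had the event. With repeated episodes, "cumulative duration across all episodes will be used adjusting for any overlap". For an "AE that was ongoing at the time of analysis, the time is censored at the last available on treatment visit date". The section closes with its analysis: "Descriptive statistics will be presented for time to AE onset (days), time to Grade 3 or 4 AE onset, and duration of AEs", in the subgroup with the event.

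SAP 5.2.15 gives the general meaning of such a summary: "Continuous variables will be summarized using descriptive statistics ie, number of non-missing values and number of missing values", followed by mean, median, standard deviation, range and quartiles. Nothing there uses a censoring indicator. SAP 5.2.17 states that "Time to event endpoints will be summarized using the Kaplan-Meier method", but 6.5.1.1 neither refers to it nor calls AE duration such an endpoint.

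Under SAP 6.5, "summaries of AEs and other safety parameters will be based on the safety analysis set by Cohort and Total". The tables in 6.5.1 and 6.5.1.1 cover incidence, grade, seriousness, relatedness, action taken, onset and duration. None counts AESIs that are ongoing or unresolved.

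SAP 3.5.2 gives CNS events (mood, speech, cognition) as the example of AESIs. For CNS effects, Protocol 1.2.3.4 reports that the earlier experience was "generally considered mild (Grade 1 and Grade 2) in severity and transient, and improved upon dose delay and/or dose reduction".

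**The concern.** A censored duration says only that the event lasted at least that long. Once such values enter an ordinary mean beside completed durations, the table treats them as event lengths. A reader cannot tell how many are minimum durations, or how many patients still had the event at cut-off.

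Elsewhere the SAP handles this openly. Duration of response (6.2.3) uses Kaplan-Meier and, if progressions are few, counts censored subjects by length of response. PFS (6.2.6) and OS (6.2.7) tabulate censoring reasons. AESI duration has no counterpart.

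What is at stake is the reading of one safety table: whether CNS effects resolved, and how long they lasted. AESI duration is not a named endpoint and feeds no decision.

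**Working it through.** The plan states no figure for AESI duration, so there is nothing to reproduce. The check covers direction first, then size under stated assumptions.

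**Direction.** Let T be the full duration of an episode and C the time from onset to the censoring date. The planned variable uses min(T, C), which never exceeds T and is shorter whenever the event is ongoing at C. The mean is therefore too low as soon as one event is ongoing. The median is unchanged if every censored value is at or above the true median.

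**One episode per patient.** Assume T is exponential with mean μ, C is independent of T, and p = P(T > C). Then E[min(T, C)] = (1 − p) × μ, so the mean is low by the fraction p. With 5%, 10% or 20% ongoing, it is 5%, 10% or 20% low.

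**The planned variable is cumulative.** Suppose a patient has k episodes of equal mean μ and only the last can be ongoing, with probability p. Full duration averages kμ and the expected loss is pμ, so the relative shortfall is pμ / kμ = p/k. With p = 20% and k = 2, it is 10%.

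**Plausible p.** Follow-up after onset is an assumption. SAP 2 puts cut-off at about 8 months after the last subject's first dose. Earlier patients have longer; late onset, death or new therapy shortens it. Take C uniform on (a, b) months and true median m. Then p = (2^(−a/m) − 2^(−b/m)) / ((b − a) × ln 2 / m).

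Example with a = 6, b = 18, m = 2: (0.1250 − 0.0020) / (12 × 0.6931 / 2) = 0.1230 / 4.159 = 3.0%.

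| Follow-up after onset | True median (months) | Ongoing, p (= mean shortfall, one episode) | Mean shortfall, two episodes (p/2) | Median |
|---|---|---|---|---|
| 6–18 months | 0.5 | 0.0% | 0.0% | unchanged |
| 6–18 months | 1 | 0.2% | 0.1% | unchanged |
| 6–18 months | 2 | 3.0% | 1.5% | unchanged |
| 6–18 months | 3 | 8.5% | 4.2% | unchanged |
| 3–15 months | 0.5 | 0.1% | 0.0% | unchanged |
| 3–15 months | 1 | 1.5% | 0.8% | unchanged |
| 3–15 months | 2 | 8.4% | 4.2% | unchanged |
| 3–15 months | 3 | 16.9% | 8.5% | unchanged |

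"Unchanged" refers to the single-episode median: no censoring time in these scenarios lies below the true median.

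**Sensitivity to shape.** With single-episode Weibull durations (shape 0.7 to 1.5) and follow-up of 6–18 months, simulation gives a mean about 5–18% low at 10% ongoing and 12–33% low at 20% ongoing.

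**Long-lasting events.** If the true median were 90 days and follow-up only 60–240 days, 34% would be ongoing. The simulated mean is then 86 days against 130, and the median 78 against 90. These inputs fit poorly with transient effects.

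**Row sizes.** Treatment-related cognitive, mood and speech effects "have been observed in 21.7%, 15.3%, 8.1% patients in the 100-mg pooled group of Study 1001". If those rates carry over:

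- Cohort 1: 66 × (0.217, 0.153, 0.081) = 14.3, 10.1, 5.3 patients.
- Cohort 2: 34 × the same rates = 7.4, 5.2, 2.8.
- Total: 100 × the same rates = 21.7, 15.3, 8.1.

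One ongoing patient is then about 1/14 to 1/5 (7–20%) of a Cohort 1 row. That is a share of patients, not a bias. It shows why a count informs even when the bias is negligible.

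**The case against.** The best defence is that the text is less definite than the concern. Section 6.5.1.1 says censored, which is time-to-event language. Section 5.2.17 offers Kaplan-Meier and the number with an event, which would reveal the unresolved share. But 6.5.1.1 does not invoke 5.2.17 and names descriptive statistics instead, so pooling is the likelier reading, though not a certain one.

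Second, time observed with the event up to a cut-off is a legitimate quantity. That stands: the number can be kept if it is labelled for what it is.

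Third, unresolved events can be traced. Continuing toxicity is followed up (Schedule of Activities, footnote 27), and the on-treatment period extends to end of follow-up or new anti-cancer drug therapy (SAP 3.5). Each AE is listed with its outcome (Protocol 9.5.1), listing dates come from the CRF (SAP 5.3.1), and imputed values are flagged (SAP 5.3). These provisions reduce the problem and allow a hand count, but they do not change the table.

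Three stronger readings are tempting, and the documents do not support them:

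- *The mean is low by the fraction ongoing.* That holds for single exponential episodes. The planned variable is cumulative, and p/k applies under the assumptions above.
- *The bias is large and the median is distorted.* The only evidence in the documents points to short events. In the exponential scenarios tabulated above the median does not move.
- *The stop-date rules conflict.* SAP 5.3.1 imputes a stop date for ongoing AEs that can differ from the 6.5.1.1 date. The rule specific to this variable most naturally governs, so this needs only a clarifying sentence.

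**Conclusion.** The point holds as a minor one. Following 6.5.1.1 as written mixes minimum and completed durations, understates mean cumulative duration whenever an event is ongoing, and leaves the number unresolved out of every planned table. The direction follows from the definition. The size is not in the documents and rests on assumed duration shape, follow-up after onset, independent censoring and number of episodes. With true medians up to 2 months and 6–18 months of follow-up, the exponential mean is at most about 3% low. Given effects described as mostly mild and transient, a small bias is the fair expectation.

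The row sizes are also assumptions: they borrow Study 1001 treatment-related rates, and the final AESI term list is not given. AE incidence, grade, seriousness and dose-action tables are unaffected, as is the primary ORR analysis.

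**What to change.** In SAP 6.5.1.1:

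1. Report, by Cohort and Total, the number and percent of AESI patients whose event is unresolved at cut-off, including those who died with it unresolved.
2. Keep the cumulative duration but label it *observed duration to cut-off*. Either identify ongoing values as minimum durations, or summarize resolved and ongoing patients separately.
3. As a clarification, state that the 6.5.1.1 censoring date takes precedence over the 5.3.1 imputed stop date for this variable, and that an imputed stop date is not a resolution date.
4. Optionally, where numbers allow, add a Kaplan-Meier summary of first-episode duration per 5.2.17, stating its assumption of independent censoring (death, new therapy). It would supplement the cumulative measure, not replace it.

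The cost is one row and one label per AESI category plus one sentence, with no new data. Durations may read as less favourable once unresolved events are shown. The optional Kaplan-Meier intervals would be wide at these row sizes.

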6.5.2. Deaths

The frequency (number and percentage) of patients in the safety analysis set who died and who died within 28 days after last dose of study treatment as well as the primary reason for death, will be tabulated based on information from the ‘Notice of Death’ and ‘Survival Follow-Up’ CRFs, by Cohort.

The frequency (number and percentage) of patients in the safety analysis set who died during follow-up period after 28 days after the last dose of study treatment will also be provided.

Date and cause of death will be provided in individual patient data listing together with selected dosing information (study treatment received, date of first/last administration, dose).

6.5.3. Laboratory Data

Laboratory results will be converted to International System of Units (Système International d'unités, SI) units which will be used for applying toxicity grades and for all summaries.

As described in [Section 3.4](#), baseline will be defined as the last assessment performed on or prior to date of the first dose of study treatment. If there are multiple assessments that meet the baseline definition on the same day without the ability to determine which was truly last, then the worst grade will be assigned as the baseline grade. Since a few CTCAE terms (including Hypo/Hypercalcemia and Activated Partial Thromboplastin) can be derived using several laboratory tests (analytes) refer to the section 2.3.7 of the “Pfizer Oncology CTCAE Grading Implementation Guidance for Laboratory Data” for determination of baseline CTCAE grade in this situation.

Additionally, laboratory results will be programmatically classified according to NCI-CTCAE version 4.03 grade. Non-numerical qualifiers will not be taken into consideration in the derivation of grade (eg, hypokalemia Grade 1 and Grade 2 are only distinguished by a non-numerical qualifier and therefore Grade 2 will not be derived). In summary statistics the number and percentage of patients corresponding to grades that only include non-quantitative criteria will be displayed as a blank or NA (not assessed) rather than 0. If there is any overlap between grade criteria (eg, CTCAE grading criteria for Creatinine Increased - a value can fall into one range based on comparison to ULN and another range based on comparison to baseline), the highest (worst) grade would be assigned to that record. Grade 5 is defined in the CTCAE criteria guidance as an event with an outcome of death. Since laboratory data does not collect an outcome, Grade 5 is not used when programmatically grading laboratory data.

Grade 0 or Outside Toxicity Reference (OTR) is not defined specifically by in the CTCAE guidance. However, programmatically this is used as a category to represent those patients who did not meet any of the Grades 1 to 4 criteria. If the laboratory value is evaluable for CTCAE criteria grading (numeric value is present, valid units and ranges are present as required to allow conversion to standard units and grading), and does not qualify for any of the Grade 1-4 criteria for a given lab test, then the value is assigned as Grade 0 or OTR.

Abnormalities will be described using the worst grade by scheduled timepoint and overall. Worst grade by scheduled timepoint will be determined using only central laboratory results. Worst case overall will be determined using both central and local laboratory results from scheduled and unscheduled visits. Several laboratory tests have bi-directional grading criteria defined so that both low (hypo) and high (hyper) values can be graded separately. Each criterion will be summarized separately. In the cases where a value is graded as a Grade 1, 2, 3, or 4 for one of the directions, that value will also be assigned as a Grade 0 for the opposite direction for that test. For example, a value meeting the criteria for Grade 3 Hypercalcemia will be classified as a Grade 0 Hypocalcemia. For CTCAE terms that can be derived using one of several laboratory tests, the maximum post-baseline grade for a given patient and CTCAE term will be the maximum across all possible laboratory tests.

For WBC differential counts (total neutrophil [including bands], lymphocyte, monocyte, eosinophil, and basophil counts), the absolute value will be used when reported by the lab. When only percentages are available (this is mainly applicable for neutrophils and lymphocytes, because the CTCAE grading is based on the absolute counts), the absolute value is derived as follows:

$$\text{Derived differential absolute count} = (\text{WBC count}) \times (\text{Differential \%value}/100)$$

If the investigator reports both the absolute and % value for Neutrophils or Lymphocytes from the same laboratory sample date and patient, ONLY the absolute value will be graded. The % value will not be graded in this scenario.

If the % value is converted to the differential absolute count for grading and the LLN for the differential absolute count is not available (only LLN for % is available) then Grade 1 will be assigned if the following conditions are met:

- Lymphocyte count decreased:
 - derived absolute count does not meet Grade 2-4 criteria, and
 - % value < % LLN value, and
 - derived absolute count $\geq 800/\text{mm}^3$.
- Neutrophil count decreased:
 - derived absolute count does not meet Grade 2-4 criteria, and
 - % value < % LLN value, and
 - derived absolute count $\geq 1500/\text{mm}^3$.

For calcium, CTCAE grading is based on Corrected Calcium and Ionized Calcium. Corrected Calcium is calculated from Albumin and Calcium as follows:

- Corrected Calcium (mg/dL) = Calcium (mg/dL) – 0.8 [Albumin (g/dL)-4].

Laboratory toxicities will be tabulated using descriptive statistics (number of patients and percentages):

- Shift table will summarize baseline CTCAE grade versus the worst post-baseline CTCAE grade.

Liver function tests: Alanine aminotransferase (ALT), aspartate aminotransferase (AST), Alkaline Phosphatase (ALP), and total bilirubin (TBILI) are used to assess possible drug induced liver toxicity. The ratios of test result over the ULN will be calculated and classified for these three parameters during the on-treatment period.

Summary of liver function tests will include the following categories. The number and percentage of patients with each of the following during the on-treatment period will be summarized by treatment arm:

- ALT $\geq 3 \times \text{ULN}$, ALT $\geq 5 \times \text{ULN}$, ALT $\geq 10 \times \text{ULN}$, ALT $\geq 20 \times \text{ULN}$;

- $AST \geq 3 \times ULN$, $AST \geq 5 \times ULN$, $AST \geq 10 \times ULN$, $AST \geq 20 \times ULN$;
- $(ALT \text{ or } AST) \geq 3 \times ULN$, $(ALT \text{ or } AST) \geq 5 \times ULN$, $(ALT \text{ or } AST) \geq 10 \times ULN$, $(ALT \text{ or } AST) \geq 20 \times ULN$;
- $TBILI \geq 2 \times ULN$;
- Concurrent $ALT \geq 3 \times ULN$ and $TBILI \geq 2 \times ULN$;
- Concurrent $AST \geq 3 \times ULN$ and $TBILI \geq 2 \times ULN$;
- Concurrent $(ALT \text{ or } AST) \geq 3 \times ULN$ and $TBILI \geq 2 \times ULN$;
- Concurrent $(ALT \text{ or } AST) \geq 3 \times ULN$ and $TBILI \geq 2 \times ULN$ and $ALP > 2 \times ULN$;
- Concurrent $(ALT \text{ or } AST) \geq 3 \times ULN$ and $TBILI \geq 2 \times ULN$ and $ALP \leq 2 \times ULN$ or missing.

Concurrent measurements are those occurring on the same date.

Categories will be cumulative, ie, a patient with an elevation of $AST \geq 10 \times ULN$ will also appear in the categories $\geq 5 \times ULN$ and $\geq 3 \times ULN$. Liver function elevation and possible Hy's Law cases will be summarized using frequency counts and percentages.

An evaluation of Drug-Induced Serious Hepatotoxicity (eDISH) plot will also be created, with different symbols for different treatment arms, by graphically displaying:

- Peak serum $ALT(/ULN)$ vs peak total bilirubin ($/ULN$) including reference lines at $ALT=3 \times ULN$ and total bilirubin= $2 \times ULN$.
- Peak serum $AST(/ULN)$ vs peak total bilirubin ($/ULN$) including reference lines at $AST=3 \times ULN$ and total bilirubin= $2 \times ULN$.

In addition, a listing of all $TBILI$, ALT , AST and ALP values for patients with a post-baseline $TBILI \geq 2 \times ULN$, $ALT \geq 3 \times ULN$ or $AST \geq 3 \times ULN$ will be provided.

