7.4.2. Laboratory Safety Assessment

Hematology, blood chemistry, and urinalysis will be collected at the time points described in the [SCHEDULE OF ACTIVITIES](#) table and analyzed at local laboratories. They may also be performed when clinically indicated and relevant results reported in the CRF as ‘unplanned visits’. The required laboratory tests are listed in [Appendix 4](#).

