Appendix 4. Required Laboratory Tests

Hematology	Chemistry Panel	Urinalysis [§]	Coagulation Tests
Hemoglobin	ALT ¹	Protein, glucose and blood	PT or INR
Platelets	AST ¹		aPTT
WBC	Alkaline Phosphatase	Urine dipstick for urine protein: If positive, and clinically indicated, collect 24-hour and microscopic urinalyses (Reflex Testing)	
Absolute Neutrophils ²	Sodium		
Absolute Lymphocytes ²	Potassium		
Absolute Monocytes ²	Magnesium		
Absolute Eosinophils ²	Chloride		
Absolute Basophils ²	Calcium		
	Total Bilirubin ¹		
	BUN or Urea ¹		
	Creatinine ¹		
	Glucose ¹		
	Phosphorus or Phosphate		
	Albumin ¹		
Lipids¹	Total Protein ¹	Pregnancy Tests	
Total Cholesterol ¹	Uric Acid ¹	For female patients of childbearing potential, serum or urine	
LDL ¹	Amylase ^{^1}		
HDL ¹	Gamma glutamyl transferase (GGT)		
Triglycerides ¹	Lactate dehydrogenase (LDH)		
	Lipase ¹		
Infections			
HBV, HCV (Screening only and if clinically indicated in case infection status is unknown)			

Potential Hy's Law cases, in addition to repeating AST and ALT, laboratory tests should include albumin, creatine kinase, total bilirubin, direct and indirect bilirubin, gamma glutamyl transferase, prothrombin time (PT)/INR, total bile acids, alkaline phosphatase, and acetaminophen levels and/or protein adduct levels.

[^] Serum total amylase (pancreatic isoenzyme required if serum total amylase >1.5x ULN per local institutional ranges (ie, CTCAE Grade >1)).

[§] Urinalysis: Dipstick is acceptable. Microscopic analyses if dipstick abnormal and/or if this is the local standard.

1. The laboratory results in fasted condition are suggested as applicable per CTCAE version 4.03 guidelines.
 2. If absolute values are not reported as per local laboratory standard practice, percentages (%) are acceptable.
- ALT=alanine aminotransferase, aPTT=activated partial thromboplastin time, AST=aspartate aminotransferase, BUN=blood urea nitrogen, GGT=gamma-glutamyltransferase, HDL=High density lipoprotein, INR=international normalized ratio, LDH=lactate dehydrogenase, LDL=Low density protein, WBC=white blood cell.

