3.5.3. Laboratory Data

Hematology, chemistry, lipids, coagulation and urinalysis result will be programmatically graded according to the NCI CTCAE version 4.03 for relevant parameters. A shift summary of baseline grade by maximum post-baseline grade will be presented. Parameters which cannot be graded will be summarized relative to the normal range (ie, normal range high or normal range low). Additional details are provided in [Section 6.5.3](#).

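### SAP 6.5.3 draws the by-timepoint worst laboratory grade from central laboratory results only, but the protocol has safety samples analyzed locally and neither document describes a central safety laboratory

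*SAP*

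**What the plan says.** SAP 6.5.3 (Laboratory Data) commits to two views of laboratory toxicity: "Abnormalities will be described using the worst grade by scheduled timepoint and overall". It then gives each view its own data source.

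- By timepoint: "Worst grade by scheduled timepoint will be determined using only central laboratory results".
- Overall: "Worst case overall will be determined using both central and local laboratory results from scheduled and unscheduled visits".

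SAP 3.5.3 lists what is graded: "Hematology, chemistry, lipids, coagulation and urinalysis result will be programmatically graded according to the NCI CTCAE version 4.03 for relevant parameters".

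Protocol 7.4.2 (Laboratory Safety Assessment) says where the samples go. It opens with "Hematology, blood chemistry, and urinalysis will be collected at the time points described in the" Schedule of Activities, and the same sentence ends with "table and analyzed at local laboratories". Appendix 4 to the protocol also assumes site laboratories. On differential counts it says "If absolute values are not reported as per local laboratory standard practice, percentages (%) are acceptable", and on amylase it says "pancreatic isoenzyme required if serum total amylase >1.5x ULN per local institutional ranges".

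**The concern.** The SAP rule keeps only central results for the by-timepoint grade, while the protocol says the scheduled samples are analyzed locally. If both statements are followed, the filter removes the records it is meant to summarize.

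What is at stake is a description of timing. The Schedule of Activities collects hematology, chemistry and lipids on Days 1, 8 and 15 of Cycle 1 and on Day 1 of later cycles. A grade by scheduled timepoint is the laboratory summary in the SAP that would use that schedule; the worst-overall grade and the shift table collapse it. Timing is relevant for this drug: protocol 5.5.1 notes that lipid elevations tend to appear early in treatment and can worsen from one cycle to the next if no statin is given.

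A programmer would have either to deliver an empty output or to depart from the SAP without instruction. SAP section 2 requires any such departure to be described in the Clinical Study Report.

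**Working it through.** No arithmetic applies: the plan states no figure on this point, and the question does not depend on a rate, an effect size or a sample size. The check is to compare the source rule with every place that says where safety samples are analyzed.

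**Step 1. Which records the SAP rule admits.** For the by-timepoint grade, a record must be (a) at a scheduled timepoint and (b) a central laboratory result. For the overall grade, central or local results count, from scheduled or unscheduled visits.

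**Step 2. Which records the protocol generates.**

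| Panel | Graded under SAP 3.5.3 | Named as local in protocol 7.4.2 | Central safety laboratory described |
|---|---|---|---|
| Hematology | Yes | Yes | No |
| Blood chemistry | Yes | Yes | No |
| Urinalysis | Yes | Yes | No |
| Lipids | Yes | Not named | No |
| Coagulation | Yes | Not named | No |

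Lipids and coagulation have their own rows in the Schedule of Activities and their own headings in Appendix 4, so the sentence in 7.4.2 does not cover them expressly.

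**Step 3. Whether a central safety laboratory appears anywhere else.** In the readable text, the central facility is the independent radiology review (protocol 7.1 and 7.2). The assay laboratory in protocol 7.5 is for pharmacokinetic samples. Other text points to site data. Appendix 4 refers to local practice and local ranges. Routine results obtained before consent may be used for eligibility (protocol section 7). SAP 6.5.3 itself provides for an investigator reporting both an absolute and a percentage differential count.

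**Step 4. Intersection of steps 1 and 2.** For hematology, chemistry and urinalysis, the set of central results at scheduled timepoints is empty on the documents' own terms. For lipids and coagulation it is empty only by inference, because no source for central results is described.

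**Step 5. What does not pass through the filter.** These outputs carry no central-only condition:

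- the overall worst grade, which admits local results;
- the shift table of baseline against worst post-baseline grade (SAP 3.5.3 and 6.5.3);
- the liver-test threshold and concurrent-elevation categories, the eDISH plots and the listing of liver values for flagged patients (SAP 6.5.3);
- the adverse event tables by maximum grade (SAP 6.5.1).

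Protocol 9.5.2 asks for worst grade per test and for shift tables, without restricting the laboratory source. Both can still be produced.

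**The case against.** The strongest reply is that nothing the protocol requires is lost. Protocol 9.5.2 does not ask for a by-visit grade display, and where SAP 6.5.3 lists its tabulations it names only the shift table. The version history says that SAP 2.0 removed unneeded wording and analyses from section 6.5.3, so the sentence may be a leftover. An empty output would also be obvious at programming and could not bias a result unnoticed. All of this stands as an argument for low severity. It does not rescue the rule: the section still says that abnormalities will be described by scheduled timepoint, and the source it prescribes yields nothing.

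A second reply is that protocol section 9 lets the SAP modify the planned analyses. It does, but that permission cannot create central results that were not collected.

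Three stronger readings are tempting, and the documents do not support them.

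- A reader might infer that every safety laboratory result is documented as excluded from the by-timepoint view. Protocol 7.4.2 names three panels. Local analysis of lipids and coagulation is likely, but it is inferred from silence.
- A reader might infer that only the overall worst grade would remain. The shift table, liver-test summaries, eDISH plots, liver listing and adverse event tables remain as well.
- A reader might use the 83.7% hypercholesterolemia and 65.8% hypertriglyceridemia in protocol 1.2.3.4 to size the loss. Those are treatment-related adverse event frequencies in Study 1001, not laboratory grades in this trial, and they do not measure information lost here. Such events, when reported as adverse events, would still appear in this trial's adverse event tables.

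**Conclusion.** Wrong as written; minor severity. The by-timepoint worst-grade description would contain no records for hematology, blood chemistry and urinalysis and, by inference, none for lipids and coagulation. The damage is confined to that one descriptive safety display. No hypothesis, decision rule or efficacy endpoint depends on it, and the primary endpoint (centrally reviewed objective response in Cohort 1) is untouched.

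The conclusion assumes that the readable text is complete on this point, that is, that no central safety laboratory is set out in a redacted part or in a study or laboratory manual. If one exists, the display would not be empty, but it would cover only that laboratory's tests, and the SAP and protocol 7.4.2 would still need to be reconciled.

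**What to change.** In SAP 6.5.3, replace the sentence on the by-timepoint grade with wording such as: *The worst grade at each scheduled timepoint will be derived from laboratory results obtained at scheduled visits (local laboratories, per protocol 7.4.2).* In the next sentence, on the overall worst case, remove the central/local distinction and keep the scheduled/unscheduled one. That distinction fits SAP 5.2.13, which generally keeps unscheduled assessments out of by-visit tables but uses them for the on-treatment worst case.

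If a central laboratory does exist, name it, list the tests it performs, and let both sources contribute. Wording that admits only local results would then repeat the error in reverse. If the by-timepoint view is no longer wanted, delete the commitment to it instead.

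It would also help to state in the protocol or the SAP where lipids and coagulation are analyzed, since protocol 7.4.2 does not say.

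The cost is an edit to two SAP sentences. It needs no new data collection and no change to study conduct, and no other planned output changes.
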